### **9.3.5 Vital Signs**

Descriptive statistics of the observed values and change from baseline (continuous data) will be presented by treatment group and visit for each parameter.

### **9.3.6 ECG**

Available standard ECG data will be tabulated by treatment group for each visit. Descriptive statistics of the observed values and change from baseline (continuous data) will be presented by treatment group and visit for parameter. Each visit will be assessed as Normal/Abnormal and Clinically Significant/Not Clinically Significant. Shift tables in relation to the combined status from baseline to each post Baseline visit will be presented.

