4.2.3 Secondary Safety Endpoints

The secondary safety endpoints include changes in C-SSRS, blood chemistry and hematology parameters (including lymphocyte count), ALT, AST, bilirubin, eGFR, creatinine, INR and QTc interval from ECG recordings 5 hours post morning dose (time window 3.5 – 6 hours) during 28 days of study drug administration.

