6.7.1 Permanent Suspension of Study Treatment

The investigator may permanently suspend the treatment in the following cases:

- If the patient's QTc interval is > 500 msec or an increase from baseline of > 60 msec is observed (please refer to section 9.2.3 for BBB correction);
- A DDI is identified with a concomitant medication that is medically required and cannot be resolved without the discontinuation of the study medication;

- If, in the view of the investigator, the patient experiences a severe allergic reaction that cannot be explained by the administration of any other medication;
- Development of liver function abnormality, as described in section 9.2.14.3.
- Development of an AE or any medical condition, which, in the opinion of the investigator, necessitates permanent suspension of study treatment;
- Withdrawal of consent.
- If the blind is broken (only allowed in emergency situations to determine appropriate patient care)

Patients have the right to discontinue study treatment for any reason. However, unless they withdraw consent and are no longer willing to participate, they should be followed for the remainder of the trial and all (S)AEs should be reported, regardless of whether or not the event is of CV origin or occurs under the care of another physician or institution.

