8 INVESTIGATIONAL PRODUCTS, DOSE AND DURATION OF TREATMENT

8.1 *Investigational Product*

CardiolRx™ is pharmaceutically produced. It contains cannabidiol in a concentration of 100 mg/ml and is free of tetrahydrocannabinol (THC; <5 ppm).

8.2 *Administration, Dosage and Duration of Treatment*

Study drug will be administered orally (via syringe)* with food according to the following treatment schedule:

Study Day	a.m. dose [mg/kg of body weight]	p.m. dose [mg/kg of body weight]
	CardiolRx™ or placebo	CardiolRx™ or placebo
1	N/A	2.5
2	2.5	2.5
3	2.5	5
4	5	5
5	5	7.5
6 - 28	7.5	7.5

At each study visit, drug accountability will be done. New bottles of study medication will be dispensed at each study visit (Days 3, 5, 7, 14 and 21).

If the next higher dose is not tolerated, the patient should return to the last tolerated dose. The highest tolerated dose will be administered until Day 28 (4 weeks post randomization).

The maximum treatment period will be 28 days.

* If the patient requires mechanical ventilation, the study medication is administered through a naso-gastric tube.

Justification for Dosing Regimen

COVID-19 is an acute illness with, at times, rapid progression of symptoms and signs. Because of this, it seems important to increase the blood level of the investigational agent as quickly as possible to achieve the potential anti-inflammatory and anti-cytokine actions that are likely to be important in this population. However, this agent has not been administered previously to this population, so care must be taken to observe closely for

adverse drug effects or drug-drug interactions that might have significant negative consequences. A similar product containing a highly purified botanical extract of CBD has been approved for use in pediatric epilepsy to a dose up to 10 mg/kg twice daily (Devinsky et al. 2016). We have chosen to restrict the maximum dose in this COVID-19 population to 7.5 mg/kg b.i.d. because of the expected elderly and perhaps frail condition of some of the enrolled patients. Investigators are encouraged to decrease the dose if there are indications of intolerance of a given dose to the previously tolerated dose.

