- Study drug dose adjustment to 7.5 mg/kg b.i.d., if 5.0 mg/kg b.i.d. is well-tolerated (If 5.0 mg/kg b.i.d. is not tolerated, then dose decrease back to 2.5 mg/kg b.i.d.)
- Study drug accountability
- Retention of frozen samples for hs-troponin, NT-proBNP, d-dimer, hs-CRP, ferritin, TNF-alpha, IL-1 beta, IL-6, IL-10 and additional parameters of interest
- Retention of frozen samples for CBD levels

Day 7

- Clinical assessment
- Vital signs, including HR, blood pressure and weight
- 12-lead ECG, including QTc interval assessment 5 hours post morning dose (time window 3.5 – 6 hours)
- Assessment of Ordinal Outcome Scale
- AE and SAE recording
- Recording of changes in concomitant medications
- Study drug dose adjustment and accountability
- Local laboratory assessments, including CBC, AST/ALT, alkaline phosphatase, bilirubin, creatinine/eGFR, INR, lymphocyte count and LDH
- Retention of frozen samples for hs-troponin, NT-proBNP, D-dimer, hs-CRP, ferritin, TNF-alpha, IL-1 beta, IL-6, IL-10 and additional parameters of interest
- Retention of frozen samples for CBD levels

If the patient is discharged before Day 7, the assessments up to Day 7 will be carried out as out-patient or home visits. After Day 7, all remaining scheduled assessments will be carried out during out-patient visits.

Time windows for out-patient visits or home visits up to Day 7 are +/- 1 day; after Day 7, time windows are +/- 2 days.

Day 14

- Clinical assessment
- Vital signs, including HR, blood pressure and weight
- 12-lead ECG, including QTc interval assessment 5 hours post morning dose (time window 3.5 – 6 hours)
- Assessment of Ordinal Outcome Scale

- AE and SAE recording
- Recording of changes in concomitant medications
- Study drug dose adjustment and accountability
- Local laboratory assessments, including CBC, AST/ALT, alkaline phosphatase, bilirubin, creatinine/eGFR, INR, lymphocyte count and LDH

Day 21

- Clinical assessment
- Vital signs, including HR, blood pressure and weight
- 12-lead ECG, including QTc interval assessment 5 hours post morning dose (time window 3.5 – 6 hours)
- Assessment of Ordinal Outcome Scale
- AE and SAE recording
- Recording of changes in concomitant medications
- Study drug dose adjustment and accountability

Day 28

- Clinical assessment
- Vital signs, including HR, blood pressure and weight
- Chest X-ray
- 12-lead ECG, including QTc interval assessment 5 hours post morning dose (time window 3.5 – 6 hours)
- LVEF by echocardiography

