### **4.2.2 Safety Endpoints**

The primary safety endpoint is the number of Serious Adverse Events (SAEs) and Adverse events (AEs) which occur during the 60-day study period.

The secondary safety endpoints include changes in C-SSRS, blood chemistry and hematology parameters (including lymphocyte count), ALT, AST, bilirubin, eGFR, creatinine, INR and QTc interval from Electrocardiogram (ECG) recordings at 5 hours post morning dose during 28 days post randomization.

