### **6.5 *Handling of Unscheduled Visits***

Visit data will be presented using nominal times as collected in the eCRF. Both scheduled and unscheduled post-baseline visits will be tabulated. Unscheduled visits will be presented as 'Visit.x.xx' (e.g. Visit 3.01).

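### SAP 9.3.6 tabulates available ECGs by nominal visit without the protocol's on-drug and post-dose timing conditions, so the by-visit QTc difference may be diluted

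*SAP*

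**What the plan says.** Protocol 4.2.3 defines the endpoint as change in "QTc interval from ECG recordings 5 hours post morning dose (time window 3.5 – 6 hours) during 28 days of study drug administration". SAP 4.2.2 describes it as QTc from ECG "recordings at 5 hours post morning dose during 28 days post randomization". The 5-hour time survives, the 3.5 to 6 hour tolerance is gone, and the period now runs from randomization. SAP section 2 promises that departures from the protocol are noted. Section 10 mentions only the loss of inferential testing and the reduced reporting.

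For the analysis, SAP 9.3.6 states: "Available standard ECG data will be tabulated by treatment group for each visit". SAP 6.5 adds: "Visit data will be presented using nominal times as collected in the eCRF". The shift tables in 9.3.6 use normal or abnormal and clinical significance. No per-patient maximum and no count against a msec limit is planned.

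Three protocol provisions decide which ECGs exist. Of patients who discontinue drug without withdrawing consent, section 6.7.1 says "they should be followed for the remainder of the trial". Section 6.7.2 allows interruptions of up to 5 days. Section 9.1 says that "after Day 7, time windows are +/- 2 days", while section 8.2 states: "The maximum treatment period will be 28 days".

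**The concern.** Protocol 9.2.3 explains the ECG timing. The regulator asked for QTc at peak blood levels, and Phase I put the maximum concentration at 5 hours. An ECG taken off drug, or well away from that time, does not address the same question.

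If such ECGs are averaged into the visit means, a real prolongation looks smaller. For a safety endpoint that is the wrong direction in which to err. The problem is sharper here because crossing a QTc limit takes the patient off drug: those with the largest rises are the ones whose later ECGs are recorded without it.

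**Working it through.** The documents give no QTc effect, standard deviation, stopping rate or share of off-time ECGs, so there is no planned QTc figure to reproduce. The check compares the texts first, then shows direction and range under stated assumptions.

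**1. The three texts side by side**

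| Condition | Protocol 4.2.3 | SAP 4.2.2 | SAP 9.3.6 with 6.5 |
|---|---|---|---|
| 5 h after morning dose | yes | yes | not applied |
| 3.5–6 h window | yes | absent | not applied |
| Period | while on study drug, 28 days | 28 days from randomization | nominal visit |

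SAP 9.3.6 thus applies neither the protocol's definition nor the SAP's own. The SAP does use such rules elsewhere: actual times for the biomarker AUEC (9.2) and threshold summaries for laboratory data (9.3.4).

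**2. How off-drug ECGs can arise**

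- Patients stopped for QTc or another reason stay in follow-up, with ECGs scheduled to Day 28.
- Interruptions can last up to 5 days.
- Day 28 ± 2 covers Days 26 to 30 and dosing ends on Day 28, so 2 of the 5 permitted days follow the last dose. That counts permitted days; it is not a frequency.

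**3. Dilution of a visit mean**

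Share of the on-drug, at-peak effect retained = (1 − f)(1 − g(1 − r2)) + f·r1. Here f is the off-drug share of active-arm ECGs, r1 the residual effect off drug, g the off-time share of on-drug ECGs, and r2 the residual effect off time. All four are assumed. Protocol 9.2.14.2 equates 6 half-lives with 18 days, so one half-life is 18/6 = 3 days. If effect follows concentration, 2^(−2/3) = 63% is left two days after stopping, 2^(−7/3) = 20% after 7 days and 2^(−14/3) = 4% after 14 days.

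| f | g | r1 | r2 | Retained |
|---|---|---|---|---|
| 5% | 10% | 0.63 | 0.89 | 0.95 × 0.989 + 0.0315 = 97% |
| 10% | 20% | 0.20 | 0.75 | 0.90 × 0.95 + 0.02 = 87.5% |
| 20% | 30% | 0 | 0.50 | 0.80 × 0.85 = 68% |

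The loss is about 3%, 12% and 32%. Raising f to 30% in the last row gives 0.70 × 0.85 = 59.5%, so the inputs set the upper end.

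**4. The Day 28 window alone**

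Assume midday ECGs 17 h (Day 29) and 41 h (Day 30) after the last evening dose, and visits spread evenly over the five days. Relative to 5 h after a dose, the 3-day half-life leaves 2^(−12/72) = 0.89 and 2^(−36/72) = 0.71. The Day 28 mean keeps 0.6 + 0.2 × 0.89 + 0.2 × 0.71 = 92%. Effective half-lives of 24 h or 12 h, which appear in neither document, would give 0.6 + 0.2 × (0.71 + 0.35) = 81% and 0.6 + 0.2 × (0.50 + 0.125) = 72.5%.

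**5. Would an on-drug-only table cure it?**

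A simulation used these assumptions: baseline QTc mean 430 msec, SD 25; reading SD 15; individual full-dose effects normal, with negative values set to zero; effect proportional to dose; off-drug effect halving every 3 days; drug stopped above 500 msec or after a rise above 60 msec. Day 28 active-minus-placebo differences in msec:

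| Effect mean, SD; other stopping per visit | True | All available | On drug only |
|---|---|---|---|
| 10, 10; none | 10.86 | 9.23 | 9.35 |
| 10, 10; 3% | 10.84 | 8.01 | 9.36 |
| 10, 20; 3% | 13.89 | 8.21 | 9.76 |
| 20, 20; 3% | 21.63 | 11.03 | 14.42 |

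All-available means lose 15%, 26%, 41% and 49%. The last two exceed the range in step 3 because the stopped patients have above-average effects, which that formula ignores. Restricting to on-drug ECGs recovers only part of the loss, and almost none in the first row, because the patients stopped for QTc leave the table.

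**The case against.** A reader might infer that the SAP redefined the endpoint to admit off-drug ECGs. The text does not support that. SAP 4.2.2 still requires a recording 5 hours after the morning dose, which a patient no longer dosing cannot provide. Nor is the randomization-based period new: protocol 11.2.3 already analyses continuous outcomes to 4 weeks after randomization. Protocol 6.7.3 includes all available data from patients who withdraw, and no protocol passage excludes off-drug ECGs. Unscheduled ECGs carry their own visit label.

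The visit means are also not the only route for a signal. Protocol 9.2.3 makes limit breaches reportable as SAEs with discontinuation, so they should reach the serious TEAE and discontinuation tables in SAP 9.3.8. The protocol also plans an unblinded QTc review by the DSMC. The SAP is an abbreviated plan after early termination, with no QTc test. The Day 28 conflict comes from the protocol's scheduling, not from SAP 9.3.6.

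All of this stands and limits the point. It does not remove it. SAP 9.3.6 applies no filter, the wording change is undeclared, and SAE reports capture individual crossings rather than a shift in the mean below the limits. A descriptive table can still mislead.

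**Conclusion.** The point holds as a gap in SAP 9.3.6 and an undeclared wording change in SAP 4.2.2. Together they allow off-drug or off-time ECGs to dilute the by-visit QTc difference. The direction is secure whenever such ECGs are present and their residual effect is smaller than the on-drug peak effect. The size is not known: 3% to 32% across the three illustrative sets, more under harsher inputs, and all of it resting on assumed shares and residual effects.

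Two stronger readings are tempting. One is that dilution has been shown to occur; the documents give no counts of off-drug or off-time ECGs. The other is that on-drug ECGs should replace the planned table; that would condition on a post-randomization event and drop the patients of most interest. Confidence is moderate. The change is worth making because it is cheap and protects a safety signal.

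**What to change.** Make the change before the SAP is approved, which its section 2 places before unblinding.

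- In SAP 4.2.2, restore the period and window of protocol 4.2.3, or list the change in SAP 10.
- In SAP 9.3.6, keep the by-visit table of available ECGs.
- Add each patient's maximum on-treatment QTc and maximum change from baseline, with counts per arm against the protocol's 500 and 60 msec limits, so that patients stopped for QTc still count.
- Add a supportive by-visit table limited to ECGs 3.5 to 6 hours after a dose taken that day. If dose times were not recorded, limit it to ECGs on or before the last-dose date. Flag ECGs after the last dose as off-drug in the listing.

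Two protocol conflicts must be reconciled. One is the Day 28 visit window (9.1) against the end of dosing (6.1, 8.2). The other is the QTc limits, worded as exceeding 500 or 60 msec in 6.2 and 6.7.1 but as reaching or exceeding them in 9.2.3; the counts need one definition.

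The cost is some wording and one or two descriptive tables from ECGs already collected. The supportive table will hold fewer ECGs.

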### **9.3.7 Chest X-Ray**

Each visit will be assessed as Normal/Abnormal. Shift tables in relation to the combined status from baseline to each post Baseline visit will be presented.

### 9.3.8 Adverse Events

Adverse events are to be recorded throughout the study, beginning at the moment of informed consent. AEs will be coded using MedDRA and displayed in tables and listings by System Organ Class (SOC) and Preferred Term (PT).

Analyses of adverse events will be performed for those events that are considered treatment-emergent, where a treatment-emergent AE (TEAE) is defined as one that started, or worsened in severity or seriousness following the first dose of IMP. An AE with onset prior to the start of the administration of the first dose of study drug, or where the stop date is before the start of the administration of the first dose of study drug, or where the study drug was not started, will be considered as pre-study. In case the onset date is on the same day as the first dose of study drug and either the time of first dose or time of AE onset is missing, then AE is considered treatment-emergent.

AE intensity will be qualified as mild, moderate, or severe. Maximum severity will be assumed for an AE with missing severity. The relationship to the study drug will be qualified as related (including categories related, probably, possibly) or unrelated.

If the AE start date is missing or partial, the AE will be assigned to the appropriate period using available start date information and the stop date, if present as described above.

The following tables will be presented for AEs incidence and/or number of events will be reported as appropriate:

- Overall summary of AEs
- TEAEs by system organ class and preferred term
- Treatment related TEAEs by system organ class and preferred term
- Serious TEAEs by system organ class and preferred term
- TEAEs by system organ class, preferred term and maximum severity
- TEAEs leading to study drug discontinuation by system organ class and preferred term
- Listing of AEs
- Listing of Serious TEAEs
- Listing of AESIs
- Listing of Deaths

Adverse event incidence is counted only once per system organ class and once per preferred term. The number and percent of subjects experiencing events are reported. Outputs reported at maximum severity show the highest severity reported by a patient per system organ class and preferred term.

## 10 CHANGES TO PLANNED ANALYSES

Due to the early termination of the study no inferential testing will be performed. All summaries will be presented descriptively. Limited scope reporting is described above.

